#### **6.6.5      Vital Signs**

Vital signs including body temperature (°C), pulse rate (bpm), systolic and diastolic blood pressure (mmHg), respiratory rate (breath/min), weight (kg), and height (cm) will be obtained in accordance with the Schedule of Activities in [Table 2](#). Changes from baseline in vital signs variables will be evaluated.

#### **6.6.6      Electrocardiogram (ECG)**

ECG parameters, including heart rate as well as RR, PR, QRS, QT, and QTcF intervals will be collected according to the Schedule of Activities in [Table 2](#). Changes in ECG parameters between baseline and each subsequent scheduled assessment will be calculated.

The outcome of the overall evaluation is to be recorded as normal/abnormal in the eCRF, with any abnormalities being recorded as not clinically significant or clinically significant.

#### **6.6.7      Other Safety Assessments**

The following assessments will be performed, but will not be used to define additional safety parameters for the study: chest X-ray, physical examination, tuberculosis (TB) screening, pregnancy tests (serum or urine), viral serology, and follicle-stimulating hormone (FSH). Data from these assessments will be available in datasets and will be listed.

### **7.      STATISTICAL ANALYSIS**

#### **7.1      Data Handling Rules and Definitions, Including Handling of Missing Data**

Except where specified all continuous variables will be summarized with descriptive statistics (the number of non-missing values, mean, SD, median, first and third quartiles, minimum, and maximum). Where data have been logarithmically transformed for analysis, the summary statistics on the back-transformed data will include the geometric mean (calculated as  $\exp(m)$ , where  $m$  is the mean of the data on the log scale) and the coefficient of variation (CV; calculated as  $100\sqrt{\exp(s^2)-1}$ , where  $s$  is the SD of the data on the log scale). All categorical variables will be summarized with frequency counts and

percentages. Tabulations will be provided based on all subjects combined, as well as separately by treatment group.

Missing data will be maintained as missing in the analysis datasets, unless specified otherwise. For variables where missing data are imputed, the analysis dataset will contain a new variable with the imputed value and the original variable value will be maintained as missing.

#### Data Imputation for Primary and Secondary Efficacy Analyses

##### **1. Multiple Imputation with Fully Conditional Specification (FCS) Method**

The FCS method will be used as a sensitivity analysis for the analyses of facial IGA and facial inflammatory/noninflammatory lesion counts. FCS methods can be used to impute missing values for variables with an arbitrary missing data pattern, assuming the existence of a joint distribution for these variables. Both intermittent and monotone missing values will be imputed in the same way with regression-based predictive mean matching method. The missing values will be imputed sequentially, with all previous visits included as additional covariates.

The steps of performing a sequential regression imputation are as follows:

- a) If there is any missing value at Week 2, it will be imputed using a regression-based predictive mean matching method. For facial inflammatory/noninflammatory lesion counts, randomization seeds of 20220118 and 20220119 will be used respectively, the regression will include the covariates of age, sex, treatment group, facial IGA score at baseline (Grade 3 vs. 4), and the baseline measurement of corresponding lesion counts. For facial IGA, a randomization seed of 20220121 will be used, and the covariates included in the regression will be age, sex, treatment group, and baseline facial IGA score as a continuous variable.
- b) All remaining missing visits will be imputed sequentially by the same regression, with covariates specified above in Step (a) and the lag values (including the imputed values) from earlier visits.
- c) The imputed values will be rounded to the nearest integer for facial IGA and facial inflammatory/noninflammatory lesion counts.
- d) The linear mixed model for repeated measures (MMRM) for continuous endpoints as described in **Section 7.5.1** and **Section 7.5.2**, respectively, will be applied to each imputed dataset. For categorical endpoints, the binary outcomes will be derived from the imputed data for each patient. The Cochran-Mantel-Haenszel (CMH) test as described in **Section 7.5.2** will be used for each imputed dataset, and the effect will be measured as Prob (concordance) - Prob (discordance) by Somers'  $d$  (interpretable also as a generalized risk difference) pooled across the facial IGA strata.

One hundred independent data replications will be done with SAS PROC MI. Results across the replicated datasets will then be combined into the final estimate using SAS PROC MIANALYZE.

##### **2. Tipping Point Analyses**

As the primary analysis (MMRM) relies on the missing at random assumption, to evaluate the robustness of the primary analysis approach, a sensitivity analysis using the tipping-point approach will be conducted.

The following steps will be used to determine the tipping point:

- a) Intermittent missing values will be imputed using the Monte Carlo Markov Chain (MCMC) approach to create a monotone missing pattern. The imputation will be implemented separately for each treatment and each facial IGA stratum (Grade 3 or 4), under the assumption that different treatments and facial IGA strata may have distinct posterior distributions. The imputation will

include all the post-baseline values, with age, and baseline value of the corresponding endpoint as covariates.

- b) If there is any missing value at timepoint 1 (Week 2), it will be imputed using a regression based MI method for monotone missingness. Covariates included in the modelling are age, sex, treatment group, facial IGA score at baseline (Grade 3 vs. 4), and baseline value of the corresponding endpoint.
- c) A delta score will be added to the imputed value at timepoint 1 for subjects missing data at timepoint 1 in the imsidolimab treatment groups, thus worsening the imputed value. The delta value will start at 0 and will be increased in a repeated process until the comparison of imsidolimab to placebo is no longer significant at 0.10 level in Step (f).
- d) All remaining timepoints will be imputed sequentially by repeating Steps (b) and (c) for each timepoint, including lag values from earlier timepoints in the imputation model (lag values will include imputed values from the previous step), in addition to the covariates specified above in Step (b). Data from subjects who have already had their responses increased by delta in the previous step(s) will not be further increased by delta again since the regression on the previous value carries this increase forward. This principle also extends to the preliminary step of imputing intermittently missing visits. Thus, if an intermittent missing value is encountered for a subject in the imsidolimab treatment groups, delta adjustment will not apply for the subsequent imputations of the monotone part of the missing visits, for that subject.
- e) For each imputed dataset, perform the same primary analysis (MMRM) as described in **Section 7.5.1** to estimate treatment differences between each dose of imsidolimab and placebo. Results across the imputed datasets will then be combined using SAS PROC MIANALYZE.
- f) Step (c) to (e) will be repeated with gradually increased delta values until the tipping point is reached.

One hundred independent dataset replications will be done with SAS PROC MI. The resulting one hundred estimates of the treatment differences and standard errors will then be combined into the final estimate using SAS PROC MIANALYZE.

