## 12. APPENDIX 2 SAS CODE FOR STATISTICAL ANALYSES

This section will be completed after examining the existing data and prior to the final signoff of this SAP.

Test	Template SAS Code for Modeling (SAS Version 9.4)
Linear Repeated Measures Analysis of Covariance for the primary endpoint	<pre> PROC MIXED METHOD=REML; CLASS SUBJECT TRT VISIT BASEFIGA; MODEL Y = BASE BASEFIGA TRT VISIT / DDFM=KR SOLUTION OUTP=OUT; REPEATED VISIT / TYPE = UN SUBJECT=SUBJECT; LSMEANS TRT VISIT / PDIFF CL ALPHA=0.1; ODS OUTPUT LSMEANS=MEANS; ODS OUTPUT DIFFS=DIFF; RUN; </pre> 
Where TRT is treatment, VISIT is the study visit number, BASEFIGA is the facial IGA score at baseline, and BASE is the baseline of outcome variable.

Negative Binomial with GEE using PROC GENMOD	<pre> PROC GENMOD; CLASS SUBJECT TRT VISIT BASEFIGA; MODEL Y= BASE BASEFIGA TRT VISIT / LINK=LOG DIST=NEGBIN; REPEATED SUBJECT=SUBJECT / TYPE=UN; LSMEANS TRT VISIT / DIFF CL ALPHA=0.1; ODS OUTPUT LSMEANDIFFS = LSDIFS ESTIMATES=EST LSMEANS=LSMEANS PARAMETERESTIMATES=PE; RUN; </pre> 
Where TRT is treatment, VISIT is the study visit number, BASEFIGA is the facial IGA score at baseline, and BASE is the baseline of outcome variable.

Impute Intermittent Missing using the Monte Carlo Markov Chain (MCMC) approach	<pre> PROC MI DATA=data_in SEED=20210710 NIMPUTE=100 OUT=LESION_MONO; BY BASEFIGA TRT; /*Assuming different treatment, baseline facial IGA has different distribution*/ MCMC CHAIN=MULTIPLE IMPUTE=MONOTONE; /*Only impute intermittent missing values*/ VAR AGE BASE LESION1 – LESION5; /*Impute lesion count from Week 2 to Week 20, with age and baseline as covariates*/ RUN; </pre>

Test	Template SAS Code for Modeling (SAS Version 9.4)
Multiple Imputation with FCS Method	<pre> PROC MI MIN=0 ROUND=1 SEED=20220118;   CLASS BASEFIGA TRT SEX;   FCS REGPMM(LESION2 = LESION1 AGE SEX TRT BASE BASEFIGA );   FCS REGPMM(LESION3 = LESION1 LESION2 AGE SEX TRT BASE BASEFIGA );   FCS REGPMM(LESION4 = LESION1-LESION3 AGE SEX TRT BASE BASEFIGA );   FCS REGPMM(LESION5 = LESION1 LESION4 AGE SEX TRT BASE BASEFIGA );   VAR LESION1 - LESION5 AGE SEX TRT BASE BASEFIGA; RUN; Add 'MAX=4' in the PROC MI statement if response variable is facial IGA score. </pre>
Combine Parameter Estimates for LSmeans	<pre> PROC MIANALYZE DATA=OUTREG;   BY VISIT;   MODELEFFECTS TRT; /* TRT IS THE VARIABLE FOR LS TREATMENT DIFFERENCES */   STDERR TRTERR; /* TRTERR IS THE STANDARD ERROR FOR TREATMENT DIFFERENCES */ RUN; </pre>

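### Tipping-point step (d) gives no delta to imsidolimab dropouts who had an earlier missed visit, so the tipping delta can be overstated

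*SAP*

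**What the plan says.** SAP 7.5.4 lists the tipping-point analysis as a sensitivity analysis of the primary endpoint, and SAP 7.1 gives its steps. It is there because the primary MMRM assumes data missing at random (MAR).

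- Step (a): "Intermittent missing values will be imputed using the Monte Carlo Markov Chain (MCMC) approach to create a monotone missing pattern". No delta is mentioned. The matching template in Appendix 2 carries the comment "Only impute intermittent missing values" and contains no shift.
- Step (b) then imputes by regression what is still missing at the first visit.
- Step (c): "A delta score will be added to the imputed value at timepoint 1 for subjects missing data at timepoint 1", in the imsidolimab groups only.
- Step (d) repeats (b) and (c) visit by visit and adds delta once per subject. A subject already shifted "will not be further increased by delta again since the regression on the previous value carries this increase forward". The step continues: "This principle also extends to the preliminary step of imputing intermittently missing visits". It concludes that, for an imsidolimab subject with an intermittent missing value, "delta adjustment will not apply for the subsequent imputations of the monotone part of the missing visits, for that subject".
- Step (f): "Step (c) to (e) will be repeated with gradually increased delta values until the tipping point is reached".

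**The concern.** Adding delta once is sound when the value before the next missing visit is itself an imputed, shifted value, because the regression then passes the shift on. Step (d) applies the same reasoning to subjects whose gap was filled in step (a), where nothing was shifted. Take an imsidolimab subject who misses Week 4, attends Week 8 and then drops out. The Week 4 value is an MAR draw, the Week 8 value is observed, and Week 12 is imputed with no delta. However large delta becomes, this subject's Week 12 value does not worsen.

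The FCS multiple imputation also listed in SAP 7.5.4 uses no delta, so this is the only planned check of the primary endpoint that departs from MAR. Its error can run in one direction only: a larger tipping delta, and a result that looks more robust than it is.

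**Working it through.** **Inputs.** SAP 3.5 gives 120 subjects randomised 1:1:1 (40 per arm), 10% discontinuing before Week 12 (4 per arm, leaving 36), difference 6.1, SD 10.4 and two-sided alpha 0.10. SAP 7.1 sets the tipping criterion at the 0.10 level. The number k of imsidolimab dropouts with an earlier gap is not in the documents and is assumed.

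**Plan's own figure.** Power for 6.1 with SD 10.4 and 36 per arm is 79.4% by the noncentral t and 80.1% by the normal approximation. The stated 80% reproduces.

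**Does any step shift an exempt subject?** Step (a): no. Steps (b) and (c): delta follows the regression, which imputes only values still missing, so a gap already filled is not reached. Step (d): exempt. Step (f): repeats (c) to (e), so (a) is not rerun. The answer is no.

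**Closed form.** Write differences as benefit over placebo. Assume that each shifted dropout moves by the full delta at Week 12 and that the standard error stays fixed.

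- SE = 10.4 × √(2/36) = 2.451. With t(70) = 1.667, the critical difference is 4.086.
- The arm mean moves by delta × (4 − k)/40, so tipping delta = (6.1 − 4.086) × 40/(4 − k).
- k = 0: 20.1. k = 1: 26.9 (×1.33). k = 2: 40.3 (×2). k = 3: 80.6 (×4). k = 4: no tipping point exists.

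**Simulation of k = 1** (Week 4 missed, Week 8 attended, then dropout; correlation assumed AR(1) 0.7 or exchangeable 0.6; Rubin's rules). If all four dropouts were last seen at Week 8, the tipping delta as written against delta at the first monotone-missing visit is 23.2 against 18.2 (AR(1)) and 23.0 against 18.1 (exchangeable), about ×1.27. A separate, simpler simulation with an unadjusted Week 12 comparison gives 22.5 and 23 against 17.5. If the four were last seen at Weeks 8, 8, 4 and 2, the figures are 30.3 against 21.9 and 39.0 against 25.9 (×1.4 and ×1.5), because earlier dropouts pass only part of their delta to Week 12.

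**How likely is an exempt subject?** Assume that visits are missed independently with probability p, and that the last attended visit is equally likely to be baseline, Week 2, 4 or 8. A gap is possible only for the last two: probability p if Week 4, 2p − p² if Week 8. Per dropout this is (3p − p²)/4 = 0.037, 0.073 and 0.140 for p = 5, 10 and 20%. At least one of four: 14, 26 and 45%. Two or more: 0.8, 2.9 and 9.7%.

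**When would the reading change?** The SAP sets no plausibility limit for delta. Taking the planned 6.1 as an illustrative yardstick, one exempt subject moves the tipping delta across it only for an observed difference between 4.086 + 6.1 × 3/40 = 4.54 and 4.086 + 6.1 × 4/40 = 4.70. At 4.6 (p = 0.065), for example, it goes from 5.1 to 6.9.

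**The case against.** Four objections have weight.

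- **The effect is conditional.** On the assumed miss rates, the most likely number of exempt subjects per arm is zero (86, 74 and 55%). The plan also has rules that reduce gaps: rescheduling of missed visits (Protocol 7.3), virtual or home visits (Protocol 4.5), and contiguous analysis windows with unscheduled data as back-up (SAP 6.2.1). This stands. A reader might infer that the tipping delta will be overstated in this trial, but the documents do not support that.
- **It seldom matters.** With SE 2.451, an observed difference falls in the 4.54 to 4.70 band with probability 2.1% if the true difference is 6.1, and at most 2.5% otherwise. Multiplied by 14 to 45%, that is about 0.3 to 1.1% per comparison. At the planned effect, every tipping delta above is about three times 6.1 or more, under either rule. This stands and limits the severity.
- **Appendix 2 is unfinished template code.** Its silence on delta shows little. This also stands, but the point rests on the prose of steps (a) to (f).
- **Delta on gap-filled values may have been intended and left out.** The wording of step (d) allows this. It does not rescue the rule, because an observed, unshifted visit lies between gap and dropout. With delta on the gap-filled value and all four last seen at Week 8, the simulated tipping delta is 23.1 (AR(1)) or 21.6 (exchangeable), still well above about 18.

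**Conclusion.** Wrong as written, and minor. The exemption rests on a carry-forward that cannot occur for the subjects it covers. If at least one imsidolimab dropout has an earlier gap and the comparison is significant at delta 0, the tipping delta is too large: about 27 instead of 20 lesions with one of four exempt, on the plan's figures and the closed-form assumptions. With none exempt there is no effect. That 0 or 1 per arm is likely rests on assumed miss rates and dropout times, not on the documents.

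Two stronger readings should be resisted. A reader might infer that the primary result is in doubt. It is not: the MMRM estimate and p-value do not use this imputation. A reader might also see a fault in the gap-filling running to Week 20, so that a missed Week 12 before an attended Week 20 receives no delta. Step (a) and the template agree on this, and MAR for a subject who returned is defensible, so it is a choice and not an error.

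**What to change.** In step (d) of SAP 7.1, delete two consecutive sentences: the one reading "This principle also extends to the preliminary step of imputing intermittently missing visits" and the next, which ends with the exemption quoted above. State instead that delta is added once, at the first monotone-missing visit of every imsidolimab subject, whether or not an earlier visit was missed and filled in step (a). The rule against adding delta twice stays, since it is correct for consecutive monotone-missing visits.

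The cost is a two-sentence edit before the analysis is run. The one downside is that the reported tipping delta may be smaller.

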#### Data Imputation for Adverse Events Summaries by Relationship to Study Drug

For the AE summaries by relationship to study drug, an AE with a missing relationship to study drug will be deemed as definitely related. Imputed values will not be listed in data listings.

#### Use of Data from Unscheduled Assessments for Laboratory, ECG, and Vital Sign Summaries (Continuous Parameters)

Data from unscheduled visits will be listed; duplicate unscheduled measurements will not be shown twice. If the data from the scheduled visit is missing, data from unscheduled visits that fall in the visit window of the same scheduled visit will be used. In cases where there are multiple unscheduled visits, the most recent unscheduled visit will be used.

#### Data Imputation (All Laboratory, Immunogenicity, and Biomarker Summaries)

Laboratory values of ' $>=x$ ' or ' $<=x$ ' will be taken as the value of x in the analyses. If a laboratory value is prefixed with ' $>$ ', the available original value +0.001 will be used for table summaries; if a laboratory value is prefixed with ' $<$ ', then the original value -0.001 will be used in table summaries.

#### Study Dates and Day of Assessment or Event

Study Day and Day of Assessment or Event definitions are provided in **Appendix 1, Data Handling Rules**.

### Incorrect Stratification

If there is any discrepancy between the IWRS-based and clinical-data-based stratification factor, the clinical-data-based value will be used for efficacy analyses.

## **7.2 Subject Disposition**

Disposition for all subjects will be tabulated and listed. The tabulation will include the number of subjects screened, randomized, and treated, randomized but not treated, the number of subjects completing the treatment period, and the number of subjects who complete the study (including follow-up) as well as who discontinue study early will also be presented; for subjects who discontinue, the reason for discontinuation will also be included. The number and percentage of randomized subjects included in the ITT, PP, Safety, and PK Analysis Sets will also be tabulated.

The randomization stratification factor and treatment assignment will be listed together. If there are any subjects who took study treatment other than what was randomized during the study, both the treatment assigned at randomization and actual treatment(s) received during the Treatment Period will be listed. The duration of actual treatment will also be listed.

The reason for exclusion of a subject from the PP, Safety, and PK Analysis Sets will be listed for all randomized subjects; the Coronavirus Disease 2019 (COVID-19) related reasons for exclusion from the PP Analysis Set may be considered. In addition, randomized subjects who violate the important protocol deviations will be listed.

## **7.3 Deviations**

All protocol deviations will be identified and discussed with the Sponsor during the BDRM prior to final database lock. Important protocol deviations for exclusion from the PP Analysis Set will be determined and appropriately categorized in this meeting. These are defined as potential protocol deviations that may significantly affect the reliability of efficacy study data.

All important protocol deviations will be summarized by treatment group and overall subjects for the ITT Analysis Set. All protocol deviations will be listed.

## **7.4 Demographic and Baseline Characteristics**

### **7.4.1 Demography and Physical Characteristics**

Demographics and baseline characteristics variables that are listed in [Section 6.1](#) will be summarized by treatment and all data will be provided in listings. Continuous baseline parameters (such as age, height, weight, BMI, facial inflammatory lesion counts, facial noninflammatory lesion counts, and DLQI/CDLQI total score), facial IGA, Truncal PGA, PGI-S, and SSQ will be summarized descriptively using mean, median, SD, minimum, maximum, first quartile, and third quartile. For categorical baseline and demographic parameters (such as age group, country, reproductive status, sex, ethnicity, race, smoking history, facial IGA, Truncal PGA, PGI-S, and SSQ), frequencies and percentages of subjects will be provided; baseline facial IGA will be reported by individual Grade 3 or 4.

### **7.4.2 Medical and Surgical History**

Medical and surgical history at screening will be summarized for the Safety Analysis Set and listed for the ITT Analysis Set.

#### 7.4.3 Prior and Concomitant Medications

Refer to [Appendix 1](#) for definitions of prior and concomitant medications. Prior and concomitant medications will be summarized by ATC class, preferred term, and actual treatment received for the Safety Analysis Set. In summary tables, subjects will only be reported once for the medication or for the class of drug s/he has taken. Prior and concomitant medications will be displayed in separate listings.

### 7.5 Efficacy Analyses

The ITT Analysis Set will be used as the primary analysis set for all efficacy analyses. Per protocol analyses will be performed on the primary as well as the following secondary endpoints:

- Change from Baseline in facial inflammatory lesion counts at visits other than Week 12
- Change from Baseline in facial noninflammatory lesion counts at each visit
- Change from Baseline in total facial lesion (inflammatory and noninflammatory lesions) counts at each visit
- Change from Baseline in facial IGA at each visit
- Proportion of subjects achieving a facial IGA of clear (0) or almost clear (1) with at least a 2-grade decrease from Baseline at each visit

No adjustment for multiplicity will be made.

All statistical tests will be performed at the 10% level of significance unless otherwise stated. All confidence intervals (CIs) will be reported as 2-sided 90% CIs unless otherwise stated. Descriptive statistics will be provided for the continuous variables as number of subjects, mean, SD, standard error of the mean, first and third quartiles, minimum, and maximum. Descriptive summaries of continuous variables will be shown for baseline, change from baseline to endpoint, and percent change from baseline to endpoint. All data will be listed in data listings.

